7.2 Definition for Analysis Populations

The Full Analysis Set (FAS) includes all randomized subjects who received at least 1 dose of study drug. Subjects will be included in the analysis based on the treatment group as randomized. The FAS will be used for all efficacy and Baseline analyses.

The Per Protocol Analysis Set represents a subset of the FAS and consists of all FAS subjects who did not have any major protocol violations that impact primary efficacy analysis. The primary endpoint will be analyzed in the Per Protocol Analysis Set. The Per Protocol Analysis Set will be determined prior to the respective primary analysis database lock.

The Safety Analysis Set consists of all subjects who received at least 1 dose of study drug. For the Safety Analysis Set, subjects will be assigned to a treatment group based on the treatment actually received, regardless of the treatment randomized.

7.3 Statistical Analyses for Efficacy

All efficacy analyses will be carried out for each study independently.

Analysis of the efficacy endpoints for Study 1 and Study 2 will be conducted on the FAS based on randomized treatment group. Unless otherwise specified, comparisons will be between the upadacitinib group and the placebo group. For each study, the between group comparison will be conducted using a two-sided test at significance level $\alpha = 0.05$.

For binary endpoints, point estimate for the response rate and 95% confidence interval (CI) will be reported for each randomized treatment group. Point estimate, 95% CI, and p-value for treatment comparison between upadacitinib and placebo will also be reported.

For continuous endpoints, the means at specified visits, least square means, and 95% CI of change from Baseline will be reported for each randomized treatment group. The least square means of treatment difference and associated 95% CI and p-value for treatment comparison between upadacitinib and placebo will also be reported.

For primary and secondary binary endpoints, the primary analysis method will use the composite estimand framework; the supplementary analysis will use the treatment policy estimand framework. For secondary continuous endpoints, the primary analysis method will use the treatment policy estimand framework. Details are outlined below.

Primary Efficacy Analysis

For Study 1 (bDMARD-IR AS), the primary endpoint is ASAS40 response at Week 14. For Study 2 (nr-axSpA), the primary endpoint is ASAS40 response at Week 14. The primary efficacy analysis will use

the composite estimand framework, where the Week 14 primary endpoint for both studies is defined as a composite endpoint that is achieved if a subject fulfills the following 2 components: 1) Remain in the study and on study drug through 14 weeks; and 2) Achieve an ASAS40 response at Week 14.

Corresponding to this estimand, in the primary analysis, subjects who discontinue study drug prior to Week 14 will be treated as non-responders. Missing data due to COVID-19 will be imputed using Multiple Imputation and additional missing data due to other reasons will be treated as non-responders.

All subjects in the FAS will be included in the primary efficacy analysis. Comparison of the primary endpoint will be made between the upadacitinib group and the placebo group using the Cochran-Mantel-Haenszel (CMH) test adjusting for the main stratification factor. For Study 1 (bDMARD-IR AS), the main stratification factor is hsCRP level (\leq ULN versus $>$ ULN). For Study 2 (nr-axSpA), the main stratification factor is MRI and hsCRP status (MRI+/hsCRP $>$ ULN, MRI+/hsCRP \leq ULN, and MRI-/hsCRP $>$ ULN). Rubin's method will be used to combine the results from the multiple datasets generated by the Multiple Imputation. For both studies, the same respective analysis will be conducted on the Per Protocol Analysis Set as a supplementary analysis.

Corresponding to the composite estimand, a sensitivity analysis will be conducted. Subjects who discontinue study drug prior to Week 14 will be treated as non-responders. Additional missing data including those due to COVID-19 will also be treated as non-responders. The same CMH analysis as the primary analysis will be conducted.

In addition, the following supplementary analyses will be performed using the treatment policy estimand framework. The same CMH analysis as the primary analysis will be conducted including all data as observed, regardless of adherence to study drug, with subjects missing ASAS40 response treated as non-responders. Additional sensitivity analysis using Multiple Imputation may also be conducted to handle missing ASAS40 responses.

Secondary Efficacy Analysis

For binary endpoints, similar analyses as for the primary endpoint will be conducted on the FAS.

The primary analysis of continuous endpoints will use the treatment policy estimand framework, intending to assess the treatment effect regardless of adherence to study drug. All subjects in the FAS will be included for the analysis. Comparisons between the upadacitinib group and the placebo group will be performed using the Mixed Model for Repeated Measures (MMRM) with treatment group, visit, and treatment-by-visit interaction as fixed effects and the corresponding Baseline value and the main stratification factor as the covariates. The same main stratification factors as in the primary endpoint analyses will be used. The MMRM model includes all longitudinal data as observed for subjects in the FAS, regardless of adherence to study drug.

For multiplicity-controlled secondary continuous efficacy variables, additional sensitivity analysis will be conducted corresponding the treatment policy estimand, where missing data will be imputed using Multiple Imputation. The imputation model will include demographics variables and Baseline disease characteristics, as well as longitudinal response observed at any other visits. The analysis of covariance (ANCOVA) model will be performed on each of the multiple imputed datasets adjusting for treatment, main stratification factor, and Baseline value. The ANCOVA results from the multiple imputed datasets will be combined using the Rubin's method.

Additional Efficacy Analyses

Additional efficacy variables will be summarized for all visits. For efficacy analysis of the placebo-controlled period (up to Week 14 in Study 1 [bDMARD-IR] and Week 52 in Study 2 [nr-axSpA]), similar statistical methods as for the primary and secondary endpoints will be used. For binary endpoints, comparisons between the upadacitinib group and the placebo group will be performed using the CMH test adjusting for the main stratification factor. Corresponding to the composite estimand, subjects who discontinue study drug or use rescue medication will be treated as non-responders for visits after study drug discontinuation or initiation of rescue medication. Missing data will be imputed similarly as for the primary endpoint. A sensitivity analysis will be conducted where all missing data are treated as non-responders. For continuous endpoints, comparisons between the upadacitinib group and the placebo group will be performed using the MMRM with treatment group, visit, and treatment-by-visit interaction as fixed effects and the corresponding Baseline value and the main stratification factor as the covariates. Handling of data observed after rescue will be further detailed in the SAP.

Long-term efficacy analysis will be performed similarly as described above, corresponding to the composite estimand for binary endpoints and the treatment policy estimand for continuous endpoints. For binary endpoints, supplementary analysis using the treatment policy estimand may also be conducted on all data as observed. For efficacy analysis beyond the placebo-controlled period (Week 14 in Study 1 [bDMARD-IR] and Week 52 in Study 2 [nr-axSpA]), no statistical comparison will be performed; descriptive statistics and 95% CIs will be provided. The analyses will be performed by randomized treatment sequence as described below:

1. Placebo → upadacitinib 15 mg QD
2. Upadacitinib 15 mg QD → upadacitinib 15 mg QD

Efficacy Analysis for the Remission-Withdrawal Period

For time to flare during the withdrawal period, the Kaplan-Meier (KM) curve will be provided based on as observed data. Subjects who discontinue the Remission-Withdrawal Period (prior to observed flare) will be considered censored. Subjects who receive retreatment will be considered flared. The KM estimator and associated 95% CIs for the flare-free rate during the withdrawal period will be provided. Similar analyses will also be performed for time to flare between Week 52 and Week 104 for Study 1 and Study 2 as well as for M16-098 (SELECT-AXIS 1).

For analysis of binary endpoints at scheduled visits during the withdrawal period, non-responder imputation will be used, where subjects who flare, discontinue the study, or have missing values are considered non-responders. For analysis of continuous endpoints, MMRM will be used. For all endpoints, analysis based on as observed data will also be performed. Descriptive statistics and 95% CIs will be provided. Data after retreatment will be excluded from these analyses and analyzed separately.

For subjects who receive re-treatment of upadacitinib after disease flare, analysis of endpoints after re-treatment will be based on data as observed. Change from baseline and improvement response are calculated from the retreatment baseline. Descriptive statistics and 95% CIs will be provided.

Subgroup Analysis for Efficacy

The analyses for the primary efficacy endpoint for Study 1 and Study 2 will also be performed in demographic subgroups, including age, gender, race, weight, body mass index, and geographical region, to assess the consistency of the treatment effect. Additional subgroup analyses based on Baseline disease characteristics and stratification factors will also be conducted. The treatment difference between the upadacitinib group and the placebo group will be presented with point estimate and 95% CI. No p-value will be provided for subgroup analysis.

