APPENDIX D. ACTIVITY SCHEDULE

The following table shows the required activities across Screening and subsequent study visits. Activities are applicable for Study 1 and Study 2 unless specified. The individual activities are described in detail in the operations manual ([Appendix G](#)). Allowed modifications due to the COVID-19 pandemic are detailed within the operations manual.

Study Activities Table (Applicable for Study 1 and Study 2 unless specified)

Activity	Screening	Baseline	Wk 1	Wk 2	Wk 4	Wk 8	Wk 12	Wk 14	Wk 18	Wk 24	Wk 32	Wk 40	Wk 52	Wk 64	Wk 76	Wk 88	Wk 104	Unscheduled Visit	PD Visit	30-Day F/U Visit OR Phone Call	
		Day 1																			
INTERVIEWS & QUESTIONNAIRES																					
Subject information and informed consent	✓																	✓ (Remission-Withdrawal Period only)			
Eligibility criteria	✓	✓																✓ (Remission-Withdrawal Period only)			
Medical history	✓	✓																			
Drug and alcohol history	✓																				
Prior/concomitant therapy	✓	✓	✓	✓	✓	✓	✓	✓	✓	✓	✓	✓	✓	✓	✓	✓	✓	✓	✓	✓	✓
Latent TB risk assessment questionnaire	✓												✓					✓			
Review and document pregnancy avoidance recommendations with females of childbearing potential	✓	✓	✓	✓	✓	✓	✓	✓	✓	✓	✓	✓	✓	✓	✓	✓	✓	✓	✓	✓	
PRO																					
BASDAI, Total Back Pain, BASFI, PtGA, Patient's Global Assessment of Pain	✓	✓	✓	✓	✓	✓	✓	✓	✓	✓	✓	✓	✓	✓	✓	✓	✓	✓		✓	
Nocturnal Back Pain		✓	✓	✓	✓	✓	✓	✓	✓	✓	✓	✓	✓	✓	✓	✓	✓	✓		✓	
ASQoL, SF-36		✓	✓		✓	✓		✓		✓		✓	✓				✓		✓		

Activity	Screening	Baseline	Wk 1	Wk 2	Wk 4	Wk 8	Wk 12	Wk 14	Wk 18	Wk 24	Wk 32	Wk 40	Wk 52	Wk 64	Wk 76	Wk 88	Wk 104	Unscheduled Visit	PD Visit	30-Day F/U Visit OR Phone Call
		Day 1																		
ASAS HI		✓	✓	✓	✓	✓		✓		✓			✓				✓		✓	
FACIT – F		✓		✓				✓		✓		✓	✓				✓		✓	
EQ-5D-5L		✓		✓				✓		✓			✓				✓		✓	
WPAI		✓						✓		✓			✓				✓		✓	
PED questionnaire		✓																		
Subject diary		✓	✓	✓	✓	✓	✓	✓	✓	✓	✓	✓	✓	✓	✓	✓	✓	✓	✓	
 EXAM																				
Body weight	✓	✓			✓	✓	✓	✓	✓	✓	✓	✓	✓	✓	✓	✓	✓	✓	✓	✓
Height		✓																		
Vital signs	✓	✓	✓	✓	✓	✓	✓	✓	✓	✓	✓	✓	✓	✓	✓	✓	✓	✓	✓	✓
Physical exam	✓	✓						✓		✓			✓		✓		✓		✓	
MRI of spine and SI joints (prior to or at the scheduled visit)	✓							✓									✓		✓	
12-lead ECG (annually at Week 52 and Week 104 if required by country regulatory authorities)	✓												✓				✓		✓	
AE assessment	✓	✓	✓	✓	✓	✓	✓	✓	✓	✓	✓	✓	✓	✓	✓	✓	✓	✓	✓	✓
Investigator assessments: TJC/SJC		✓						✓		✓			✓		✓		✓		✓	

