Investigator assessments: BASMI _{lin}		✓						✓		✓			✓		✓		✓		✓	

Activity	Screening	Baseline	Wk 1	Wk 2	Wk 4	Wk 8	Wk 12	Wk 14	Wk 18	Wk 24	Wk 32	Wk 40	Wk 52	Wk 64	Wk 76	Wk 88	Wk 104	Unscheduled Visit	PD Visit	30-Day F/U Visit OR Phone Call
		Day 1																		
Investigator assessments: MASES		✓			✓	✓		✓		✓			✓		✓		✓		✓	
Investigator assessments: PGA		✓	✓	✓	✓	✓	✓	✓		✓		✓	✓		✓		✓		✓	
Anteroposterior (AP) pelvis x-ray	✓																			
Lateral cervical and lumbar – spine x-ray	✓																✓		✓	
CXR (annually after Week 52 if annual TB test is newly positive [seroconversion])	✓												✓				✓			
Physical activity device dispensation (Study 1 [bDMARD-IR AS] only; except in countries where the digital health technology device is not available or is not allowed to be used in the study by the local regulatory authority) (device is to be worn through Week 14)		✓																		
Collection of physical activity device (Study 1 [bDMARD-IR AS] only; only applies to countries where the digital health technology device is approved)								✓												

Activity	Screening	Baseline	Wk 1	Wk 2	Wk 4	Wk 8	Wk 12	Wk 14	Wk 18	Wk 24	Wk 32	Wk 40	Wk 52	Wk 64	Wk 76	Wk 88	Wk 104	Unscheduled Visit	PD Visit	30-Day F/U Visit OR Phone Call
		Day 1																		
Physical activity spinal range of motion tasks (Study 1 [bDMARD-IR AS] only; only applies to countries where the digital health technology device is approved)		✓	✓	✓	✓	✓	✓	✓												
ASDAS (CRP) calculation to determine eligibility for Remission-Withdrawal Period																✓	✓			
																				
Urine pregnancy test (for all female subjects of childbearing potential)		✓	✓	✓	✓	✓	✓	✓	✓	✓	✓	✓	✓	✓	✓	✓	✓		✓	✓
Dispense urine pregnancy tests for monthly home testing									✓	✓	✓	✓	✓	✓	✓	✓				
Dispense urine pregnancy tests for monthly home testing (subjects entering OLE in applicable countries; see Appendix F)																	✓			
Erythrocyte sedimentation rate	✓	✓	✓	✓	✓	✓	✓	✓	✓	✓	✓	✓	✓	✓	✓	✓	✓	✓	✓	✓
Beta-D-glucan (Japan only)	✓																			

Activity	Screening	Baseline	Wk 1	Wk 2	Wk 4	Wk 8	Wk 12	Wk 14	Wk 18	Wk 24	Wk 32	Wk 40	Wk 52	Wk 64	Wk 76	Wk 88	Wk 104	Unscheduled Visit	PD Visit	30-Day F/U Visit OR Phone Call
		Day 1																		
 CENTRAL LAB																				
FSH, HIV, HCV, serum pregnancy test	✓																			
hsCRP, clinical chemistry, hematology, urinalysis	✓	✓	✓	✓	✓	✓	✓	✓	✓	✓	✓	✓	✓	✓	✓	✓	✓	✓	✓	✓

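### For MRI SPARCC, and for BASMI if the model stops at Week 14, the planned MMRM is an ANCOVA on observed Week 14 values, and the multiple-imputation check cannot use on-study disease course

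*Protocol*

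**What the plan says.** Protocol 7.3 (Secondary Efficacy Analysis) gives one model for all continuous secondary endpoints: comparison "using the Mixed Model for Repeated Measures (MMRM) with treatment group, visit, and treatment-by-visit interaction as fixed effects", with the Baseline value and the main stratification factor as covariates. It states "All subjects in the FAS will be included for the analysis" and adds: "The MMRM model includes all longitudinal data as observed for subjects in the FAS, regardless of adherence to study drug". No exception is made for endpoints measured at a single visit.

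For the multiplicity-controlled continuous endpoints, 7.3 adds a sensitivity analysis "where missing data will be imputed using Multiple Imputation". Its predictors are listed: "The imputation model will include demographics variables and Baseline disease characteristics, as well as longitudinal response observed at any other visits". ANCOVA is then run on each completed dataset and the results are combined by Rubin's method.

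Appendix D sets the visits:
- The row "MRI of spine and SI joints (prior to or at the scheduled visit)" is ticked at Screening, Week 14, Week 104 and the PD Visit.
- The row "Investigator assessments: BASMI" (linear) is ticked at Baseline, Weeks 14, 24, 52, 76 and 104, and the PD Visit.

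Protocol 3.3 places MRI SPARCC second among the controlled secondary endpoints in both studies (spine in Study 1, SI joints in Study 2) and BASMI thirteenth in both.

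**The concern.** An MMRM handles dropout better than a single-visit analysis because a subject's earlier values of the same endpoint inform the missing later one. That needs earlier values. The other controlled continuous endpoints have them; ASQoL, ASAS HI and MASES, for example, are each collected at Weeks 4 and 8. MRI SPARCC and BASMI have none. For these two, a subject without a Week 14 value contributes nothing to the estimate, which does not match the statement that all FAS subjects are included.

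The sensitivity analysis is meant to test the result against missing data. For these endpoints its post-baseline predictor, "as well as longitudinal response observed at any other visits", is empty before Week 14. Disease activity recorded between Baseline and dropout is not listed as a predictor.

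MRI SPARCC's rank raises the stakes. Under the fixed sequence in Protocol 7.6 it gates 14 − 2 = 12 later endpoints in Study 1, and 15 − 2 = 13 in Study 2 (12 for the FDA sequence).

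**Working it through.** **The plan's own figures.** Protocol 7.7 claims at least 80% power for the MRI endpoint but gives no effect size or SD, so that figure cannot be reproduced. The relevant input it does give is 10% dropout for Week 14 endpoints. Read as 90% of randomised subjects analysed, the primary-endpoint power reproduces: 99.8% in Study 1 (24% vs 6%, 174 per arm) and 99.6% in Study 2 (42% vs 17%, 137 per arm). Both meet the stated 90%. No stated number is in dispute.

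**Step 1: the model with one visit.** With one post-baseline observation per subject, visit has a single level and treatment-by-visit equals treatment. What remains is Week 14 change on treatment, Baseline value and stratification factor, fitted to observed values. A numerical check of one-observation GLS against ordinary ANCOVA agreed to within 1e-15 for estimates and standard errors.

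**Step 2: how many subjects.** If all of the 10% dropout became missing Week 14 values:
- Study 1: 0.10 × 386 = 38.6, so about 39 contribute nothing and 347 are analysed.
- Study 2: 0.10 × 304 = 30.4, so about 30 contribute nothing and 274 are analysed.

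The precision cost is slight. The standardised difference detectable at 80% power is (1.960 + 0.842) × √(2/n):

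| | n per arm, full | Detectable | n per arm, 90% | Detectable |
|---|---|---|---|---|
| Study 1 | 193 | 0.285 | 174 | 0.300 |
| Study 2 | 152 | 0.321 | 137 | 0.338 |

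**Step 3: what the MI check adds.** In an illustrative simulation (about 10% missing, true effect −0.30, assumed parameters):
- Values missing at random, extra baseline variables uninformative (Study 1 size): MI and observed-case ANCOVA nearly coincide, with mean absolute difference 0.005 and SE 0.086 for both.
- Missingness driven by a baseline characteristic that is in the imputation model but not in the ANCOVA: observed-case −0.212, MI −0.300 (Study 1 size); −0.210 and −0.299 (Study 2 size).

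So MI can correct for baseline-driven missingness. It cannot correct for missingness driven by something absent from its predictors.

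**Step 4: size of the gap.** Assumptions, none from the documents: SD of SPARCC change 8; correlation with ASDAS change 0.4; subjects with missing values 1 SD worse on ASDAS than those observed. The expected SPARCC difference between missing and observed subjects is 0.4 × 8 × 1 = 3.2 units. The observed arm mean looks better than the full arm mean by (share missing) × 3.2:
- 15% missing: 0.15 × 3.2 = 0.48.
- 5% missing: 0.05 × 3.2 = 0.16.
- Shift in the treatment difference: 0.48 − 0.16 = 0.32 units, or 0.32 / 8 = 0.04 SD.
- 10% in each arm: 0.32 − 0.32 = 0.

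If placebo loses more, the benefit is understated by 0.32; if upadacitinib loses more, it is overstated by 0.32.

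A simulation with SD 8, correlation 0.4, 15% vs 5% missing driven by ASDAS and a true effect of −3.0 agrees. Observed-case ANCOVA and baseline-only MI both gave about −2.66. MI with post-baseline ASDAS gave about −3.00, with almost no loss of precision.

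**The case against.** **The study SAPs may settle this.** Protocol 7.1 leaves the details to the SAP of each study. The available SAP covers only the Remission-Withdrawal Period, and its section 1.0 says the Study 1 and Study 2 SAPs are separate documents. They may already name ANCOVA, map PD values and list auxiliary variables. This stands, and the point is conditional on it.

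**A reader might infer that the MI check also drops subjects.** It does not. It imputes missing values and keeps all 386 or 304 subjects, and it uses demographics and Baseline characteristics that are not all in the MMRM. Nor must it return the same answer, as the −0.212 versus −0.300 case shows.

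**A reader might call the analysis completers-only.** Protocol 5.6 asks subjects who stop study drug to keep attending scheduled visits, and the PD Visit includes MRI and BASMI. Only subjects without a usable Week 14 value are affected. What 7.3 lacks is a rule for using a PD value.

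**Other visits do exist for BASMI.** The text does not cut the model at Week 14, and in Study 2 the Week 24 and 52 values are placebo-controlled. This has force for Study 2. In Study 1 everything after Week 14 is open-label. For MRI the only later scheduled scan is at Week 104, open-label in both studies. It would exist at the Week 14 lock only for subjects enrolled at least 104 − 14 = 90 weeks before the last one.

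**The effect is small and assumed.** This is correct. Nothing in the documents shows that missingness will be unbalanced or will follow ASDAS or hsCRP.

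**Conclusion.** The point holds in a limited form. For MRI SPARCC in both studies, and for BASMI if the model is cut at Week 14, the stated MMRM equals an ANCOVA in subjects with a usable Week 14 value, so the all-FAS statement is inexact. The MI check retains everyone but, before Week 14, has no post-baseline value of the same endpoint to draw on. It therefore cannot correct for missingness related to the on-study disease course.

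The likely bias is about 0.3 SPARCC units (0.04 SD) under the assumptions in Step 4, and about 0 with balanced missingness, in either direction. A reader might infer from MRI SPARCC's rank that the testing sequence is in danger. The documents do not support that: they give no MRI effect size, SD or missing rate, and a shift of this size is modest beside the detectable differences of 0.300 and 0.338 SD. This is a cheap improvement, not a flaw that undermines the result.

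**What to change.** Unless the Study 1 and Study 2 SAPs already do so, for MRI SPARCC and BASMI:
- Name ANCOVA at Week 14 (treatment, Baseline value, main stratification factor) as the model, and qualify the all-FAS statement to say which subjects contribute. If later BASMI values are to enter in Study 2, say so.
- In the MI already planned, impute within treatment group and add post-baseline ASDAS, hsCRP and BASDAI through Week 14 as auxiliary predictors. Appendix D already collects the BASDAI, patient global assessment and hsCRP at Weeks 1, 2, 4, 8, 12 and 14.
- State how a PD-visit MRI or BASMI value is used.
- Report the observed-case ANCOVA beside the MI result.

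The cost is SAP wording and one extra imputation model, with no new data. The enriched imputation still assumes missing at random given its predictors.

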7.7 Sample Size Determination

The sample size and power were calculated for Study 1 and Study 2 separately. Power and sample size calculations were performed at two-sided significance level of 0.05 and accounting for a 10% dropout rate for Week 14 endpoints.

Study 1 (bDMARD-IR AS)

The planned total sample size of 386 subjects for this study (with a 1:1 randomization ratio for placebo and upadacitinib 15 mg) provides at least 90% power for the primary endpoint ASAS40 response of upadacitinib 15 mg versus placebo using a two-sided Chi-square test at 0.05 level. For ASAS40, the assumed response rates for upadacitinib and placebo are 24% and 6%, respectively.^{20,26,40} This sample size also provides 90% power for ASAS20, with assumed response rates for upadacitinib and placebo of 41% and 24%, respectively.

In addition, this sample size provides at least 80% power for several of the multiplicity-controlled secondary endpoints including change from Baseline in ASDAS, change from Baseline in MRI SPARCC score of spine, BASDAI 50 response, ASDAS ID, change from Baseline in Total Back Pain, change from Baseline in Nocturnal Back Pain, ASDAS LDA, change from Baseline in BASFI, and ASAS PR.^{20,26,40}

Study 2 (nr-axSpA)

The planned total sample size of 304 for this study (with a 1:1 randomization ratio for placebo and upadacitinib 15 mg) provides at least 90% power for the primary endpoint ASAS40 response of upadacitinib 15 mg versus placebo using a two-sided Chi-square test at 0.05 level. For ASAS40 at Week 14, the assumed response rates for upadacitinib and placebo are 42% and 17%, respectively.^{38,41,42,43}

In addition, this sample size provides at least 80% power for several of the multiplicity-controlled secondary endpoints including change from Baseline in ASDAS, change from Baseline in MRI score of SI joints, BASDAI 50 response, ASDAS ID, change from Baseline in Total Back Pain, change from Baseline in Nocturnal Back Pain, ASDAS LDA, ASAS PR, and Week 52 ASAS40 response (multiplicity-controlled for EU/EMA regulatory purposes).^{38,41,43}

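### The MMRM for the continuous secondary endpoints gives Baseline one slope for all visits; adding baseline-by-visit is a minor, almost free improvement to the Week 14 comparison

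*Protocol*

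**What the plan says.** Under Secondary Efficacy Analysis, protocol Section 7.3 names the MMRM as the primary analysis of the continuous endpoints. The model contains treatment, visit and "treatment-by-visit interaction as fixed effects and the corresponding Baseline value and the main stratification factor as the covariates". All observed data enter it: "The MMRM model includes all longitudinal data as observed for subjects in the FAS, regardless of adherence to study drug". The covariance structure is not stated.

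Under Additional Efficacy Analyses the same model is repeated for the placebo-controlled period, which runs to Week 52 in Study 2: "using the MMRM with treatment group, visit, and treatment-by-visit interaction as fixed effects", again with Baseline and the main stratification factor as covariates. Neither place lists a baseline-by-visit term.

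For the multiplicity-controlled continuous endpoints, Section 7.3 adds a sensitivity analysis by multiple imputation, with an ANCOVA on the "imputed datasets adjusting for treatment, main stratification factor, and Baseline value". Applied at Week 14, that ANCOVA has its own Week 14 baseline slope.

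Section 7.1 leaves full detail to a SAP for each study. The supplied SAP covers only the Remission-Withdrawal Period (its Section 1.0). Its own MMRMs, in Sections 9.2.1.3 and 9.3.1.2, also list visit and baseline without their interaction.

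**The concern.** Read literally, one baseline slope serves every visit. That is right only if change depends on baseline equally strongly at each visit. Correlation with baseline usually weakens with time on treatment, and the slope of change then steepens from the first visit to Week 14. The fitted common slope is a compromise over visits, so it can misfit the one visit that is tested.

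Two things are at stake. The first is precision at Week 14. ASDAS is the first secondary endpoint in both studies. Section 7.7 claims at least 80% power for only some of the controlled secondaries: ASQoL, ASAS HI and MASES are not named for either study, nor BASFI for Study 2. In Study 2 those four precede Week 52 ASAS40 in the EU/EMA sequence. The second is interpretation. The MMRM and the multiple-imputation ANCOVA differ in their baseline adjustment as well as in their handling of missing data, so a gap between them could not be put down to missing data alone.

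**Working it through.** **Inputs from the documents.** 193 per arm in Study 1; "two-sided significance level of 0.05 and accounting for a 10% dropout rate for Week 14 endpoints"; visits from Appendix D. The documents give no SD, baseline correlation, slope or effect for any continuous endpoint. Those below are assumptions and are varied.

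**1. The plan's own figure.** No MMRM standard error is stated, and no inputs are given for the continuous-endpoint power. The tightest figure that can be checked is for Study 1: "This sample size also provides 90% power for ASAS20, with assumed response rates for upadacitinib and placebo of 41% and 24%, respectively".
- With 10% dropouts counted as non-responders, the rates are 0.41 × 0.9 = 36.9% and 0.24 × 0.9 = 21.6%. At 193 per arm the pooled two-proportion test has 91.4% power.
- Solving for n with continuity correction gives 169 per arm; 169/0.9 rounds up to 188, or 376 in total, within 3% of 386. Without the correction it is 158, then 176, or 352 in total.

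The stated power is reproduced. It rests on a chi-square test and does not involve the MMRM.

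**2. Endpoints exposed.** Post-baseline visits up to Week 14:

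| Endpoint | Weeks | Visits | Extra df |
|---|---|---|---|
| ASDAS (from its components), Total Back Pain, Nocturnal Back Pain, BASFI | 1, 2, 4, 8, 12, 14 | 6 | 5 |
| ASAS HI | 1, 2, 4, 8, 14 | 5 | 4 |
| ASQoL | 1, 4, 8, 14 | 4 | 3 |
| MASES | 4, 8, 14 | 3 | 2 |
| MRI SPARCC, BASMI | 14 | 1 | 0 |

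With one visit the model is an ANCOVA, so the last row is unaffected at Week 14. BASMI in Study 2 would be affected only if later visits entered the same model.

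**3. The slope.** With r_t the correlation of visit t with baseline, the slope of change on baseline is r_t × SD_t / SD_0 − 1. It is constant only if r_t × SD_t is constant. With all SDs equal to 1:
- r falling from 0.72 (Week 1) to 0.35 (Week 14) moves the slope from −0.28 to −0.65 (moderate);
- r falling from 0.82 to 0.18 moves it from −0.18 to −0.82 (extreme).

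**4. Standard error at Week 14.** With complete data, the variance ratio of common to visit-specific slopes is about 1 + (b14 − b_common)² × SD_0² / SD_resid². This was compared with maximum-likelihood MMRM simulations (six visits, unstructured covariance, 10% dropout, no stratum term).
- Moderate, SD rising to 1.3: b14 = 0.35 × 1.3 − 1 = −0.545; fitted common slope −0.32; residual variance 1.69 × (1 − 0.35²) = 1.483. Variance ratio 1 + 0.0506/1.483 = 1.034, so SE ratio 1.017. Large-sample simulation gave about 1.015.
- Moderate, constant SD: mean simulated SE at 193 per arm was 0.1025 against 0.0994, ratio 1.03.
- Extreme: b14 = −0.82; fitted common slope −0.35. Variance ratio 1 + 0.2209/0.9676 = 1.228, so SE ratio 1.108. Simulation gave about 1.10.
- Equal slopes: ratio 1.00.

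A second set of assumptions (baseline SD 0.8, Week 14 residual SD 1.0) gave variance increases of 1% for slopes from −0.30 to −0.45, 4% to 6% for −0.20 to −0.50, and 14% for −0.10 to −0.60. In SE terms these are about 0.5%, 2% to 3%, and 7%.

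**5. Power.** If power is p with the interaction, without it power is Φ((1.960 + z_p)/ratio − 1.960).

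| SE ratio | from 80% | from 90% |
|---|---|---|
| 1.015 | 78.8% | 89.1% |
| 1.03 | 77.6% | 88.2% |
| 1.10 | 72.1% | 83.8% |

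**6. Bias.** Large-sample estimates for a true difference of −0.40 in baseline SD units, moderate setting with constant SD:

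| Dropout odds ratio per baseline SD | One slope | By visit |
|---|---|---|
| 2 in both arms | −0.394 | −0.395 |
| 2 on placebo, 0.5 on upadacitinib | −0.430 | −0.402 |
| 3 on placebo only | −0.424 | −0.403 |

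Across settings the bias under arm-differential dropout was about 0.02 to 0.04 SD, or 0.15 to 0.35 SE. By normal approximation, a bias of 0.23 to 0.35 SE takes a nominal 0.05 test to about 0.056 to 0.064. The null simulations (250 replicates, odds ratios 2 and 0.5) rejected in 4.8% and 3.2% of trials with one slope. With a Monte Carlo error of √(0.05 × 0.95/250) = 1.4 points, they neither confirm nor exclude a change of that size.

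**The case against.** The strongest reply is that Section 7.3 is a summary. It omits the covariance structure too, and the study SAPs that hold the full model were not supplied. That stands as an uncertainty: nobody can say from these documents that those SAPs lack the term. The withdrawal SAP omits it as well, but its analyses have no comparator and are descriptive, so it is weak evidence either way.

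Next, a main-effect baseline covariate is a legitimate pre-specified choice and the loss is small. For a large effect it changes nothing. With residual SD 1.0 and 174 completers per arm, the SE is √(2/174) = 0.107, so a difference of 0.70 is 6.5 SE; a 14% larger variance leaves 6.1. This stands for strong effects but says less about endpoints with no stated power.

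Third, the multiple-imputation ANCOVA partly covers the issue, and Section 5.6 asks subjects who stop drug to keep attending visits, which limits missing data. Both points stand. However, the ANCOVA is a sensitivity analysis, while the MMRM is the stated primary method for these endpoints.

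A reader might infer that the one-slope model always widens the Week 14 standard error. It does not: with equal slopes there is no loss. A reader might also infer that any dropout related to baseline biases the comparison. When the relation was the same in both arms, no bias was detectable.

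**Conclusion.** The point holds as a minor improvement to the model. As written, Section 7.3 fits one baseline slope across visits for seven controlled continuous secondaries in each study. If slopes vary, Week 14 precision is lost: 1.5% to 3% in SE under moderate assumptions, up to about 10% under extreme ones, and nothing if slopes are equal. Bias needs two conditions together, slopes that vary by visit and baseline-dependent dropout that differs by arm, and is small even then.

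Every slope, SD, correlation and dropout odds ratio is assumed. The six-visit results fit ASDAS, the two pain scores and BASFI best; ASAS HI, ASQoL and MASES have five, four and three visits, so the size will differ, and for MASES no visit precedes Week 4. Nothing here supports reading the point as a threat to the primary ASAS40 analysis or to the stated sample sizes. For Study 2 after Week 14 the same model applies, but the only controlled Week 52 endpoint is binary, so the stake there is confined to uncontrolled continuous comparisons.

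**What to change.** In protocol Section 7.3, list the MMRM fixed effects as treatment, visit, treatment-by-visit, Baseline, baseline-by-visit and main stratification factor. Use this for the Week 14 controlled endpoints and for the Study 2 continuous comparisons to Week 52. State the covariance structure in the same place. Carry both into the Study 1 and Study 2 SAPs, or confirm that they are already there.

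The cost is one model term and a few degrees of freedom: five for six visits, two for MASES. No new data are needed, and no precision was lost in simulation when slopes were in fact equal. The sample size stays as it is.
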